4.2.2 Secondary Outcome Measures

Secondary outcomes include:

- Code status preferences (Aim 1)
- Use of palliative care consult/services (Aim 1)
- Hospice use (Aim 1)
- Health Care Proxy (Aim 1)

Secondary outcomes related to Aim 2a (patients 18+ years admitted to one of the study inpatient units with ADRD/delirium) include:

- Documentation of ACP Preferences in Electronic Health Record

Secondary outcomes related to Aim 2b (caregivers of patients with ADRD/Delirium) include:

- ACP knowledge (Aim 2)
- Confidence in future care (Aim 2)
- Communication satisfaction (Aim 2)
- Decisional satisfaction (Aim 2)
- Decisional conflict (Aim 2)

5 Study Design

This is pragmatic SW-CRT of a PCE-led, video-assisted COVID-19 ACP intervention in inpatient-based units (3 medical-surgical wards, Medical ICU, Cardiac ICU, Neurology ICU, step-down unit) at two hospitals: BMC and North Shore University Hospital (Northwell Health). All inpatients ≥ 65 and all patients with ADRD/Delirium ≥ 18 who are hospitalized on a unit during the intervention phase will receive the intervention.

This 2-year study (2 month data collection and tool preparation, staff training and site standardization (we are already embedded in both health systems doing similar work; thus this

short timeframe is feasible); 16 months rolling recruitment and surveying; 2 months data cleaning and analysis, and 4 months manuscript preparation and dissemination of findings) will roll out the intervention to 14 randomized inpatient units at 2 sites. Every two months, an additional inpatient unit will be added to our intervention at each hospital, i.e., there will be seven waves or "steps"; for a total of 7 units at each hospital.

Consistent with a SW-CRT with two hospital units per step (cluster), prior to the collection of any data in the pre-intervention period, we will generate a set of uniform random numbers for each of the seven clusters to be assigned to a starting period for the study intervention. There will be eight study periods in total with a usual care period at the start of the study for all clusters. The first randomized intervention period will then begin in period two.

Cluster	Baseline	14 Months of Clustered Intervention Expansion							
	M0	M2	M4	M6	M8	M10	M12	M14	
1									
2									
3									
4									
5									
6									
7									

The data needed to assess the outcomes for all patients will be derived from each hospital's EHR (Aim 1).

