For Aim 1, there are special informed consent considerations in this pragmatic SW-CRT: the hospital clinical unit is the level of randomization, the intervention is of low risk and will be implemented as the standard of care for the whole clinical unit, and data for our primary outcome and related outcomes derived from the EHR are ascertained from existing sources. Thus for this aspect of our proposal, we will seek a waiver of individual informed consent and HIPAA authorization after careful review of the criteria to do so as we have previously done successfully in prior studies. The research involves no more than minimal risk to the subjects as described above. We do not believe the waiver will adversely affect the rights and welfare of the subjects. As a pragmatic trial of thousands of hospitalized patients and clinicians, this research could not practicably be carried out without the waiver nor without access to and use of PHI of patients.

For Aim 2a, we will seek a waiver of individual informed consent and HIPAA authorization due to the fact that this is a low risk activity (chart review), and the target population is incapable of consent due to a diagnosis of ADRD/Delirium.

For Aim 2b, verbal informed consent will be obtained for the phone survey. The caregiver survey should take less than fifteen minutes.

Natural Language Processing (NLP) Data Collection

Over the course of the study, we will review the charts for all enrolled participants. For Aim 1 and Aim 2a, the inpatient EHR records (including those with ADRD/Delirium) will be analyzed (approximately 15,000 patients across both sites).

Initial NLP analyses will be done locally at each data collection site (BMC and Northwell) using software that was developed at DFCI for this purpose. The results of that initial analysis will be coded and sent as a HIPAA LDS via HIPAA approved cloud folders such as Box.com to our NLP partners at DFCI. Each site will retain a local mastercode file that will not be shared with anyone outside the institution. Patients will be assigned a unique identifier that will be used on datasets shared with DFCI.

DFCI will have a reliance agreement in place with BUMC and Data Transfer Agreements in place with both BMC and Northwell.

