11.2 Source Documents

Source documents for this study will consist of electronic health record (EHR) data from each data collection site (Boston Medical Center and Northshore Medical Center). Data generated by the methods described in the protocol will NOT be recorded in the subjects' medical records and/or study progress notes. Data may be transcribed legibly on CRFs supplied for each subject or directly inputted into an electronic system or any combination thereof.

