12.1 Study Hypotheses

Aim 1: To test the effects of a PCE video intervention leveraging video decision aids on the quality of end-of-life care. We will conduct a SW-CRT to evaluate intervention effectiveness by comparing the following outcomes among 15,000 hospitalized patients: ACP documentation; preferences for resuscitation; palliative care consults; and, hospice use. **Hypotheses:** *A higher proportion of patients in the intervention phase (vs. control) will: (1) complete advance care plans (primary outcome), (2) have documented resuscitation preferences, (3) have palliative care consults, (4) enroll in hospice over the course of one year of follow-up, and (5) have documented health care proxies.*

Aim 2: To characterize caregiver-centered outcomes of patients with ADRD/Delirium, including: (1) knowledge, (2) confidence in future care, (3) communication satisfaction, (4) decisional satisfaction, and (5) decisional conflict in 600 caregivers of patients with ADRD/Delirium admitted to the hospital. **Hypothesis:** *Intervention phase caregivers of patients with ADRD/Delirium (vs. control) will have higher knowledge, confidence, communication satisfaction, decisional satisfaction, and lower decisional conflict.*

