Primary outcome: ACP documentation. In order to formally estimate and test differences in the proportion of patients with documentation of ACP between the intervention and usual care groups, we will employ logistic regression models for correlated binary outcome data. These models will either involve the use of robust variance methods to account for the clustering of these data by hospital site and/or health system via generalized estimating equations (GEE) or the inclusion of a random effects terms (in which case, the results will be interpreted as cluster-specific). Other potential modifiers of the effect of intervention, confounding variables, or covariates can be added to this model as fixed effects. Although we do not expect effect modification in the study data, we will examine the potential for such effects (interaction) through the use of stratified analyses and the inclusion of interaction terms with study group in our statistical models. Candidate effect modifiers will be specified a priori and will include age, gender, race/ethnicity, religion, and language. We will also examine and incorporate secular trend effects, i.e., the effect of time over the course of the study. Statistically significant interactions with the intervention will be retained and the nature of heterogeneous intervention effects will be estimated using the interaction model.

Based on our prior work in which we exhibited the fact that African-American and Hispanic patients are at particularly high risk for lower level of knowledge related to ACP, not discussing ACP with family, not having a health care proxy, and not having ACP documentation, we anticipate that this intervention may be particularly beneficial for African-American and Hispanic patients.(115, 131, 132) Accordingly, we will evaluate heterogeneous treatment effects by race and ethnicity and anticipate having adequate diversity in our study population to make such assessments. All data regarding Aim 1 will come from the EHR. Our institutions maintain excellent self-report information regarding race and ethnicity.

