We will conduct analyses related to potential effect modification as a step in our model validation process and to identify relationships that can be examined more fully in future research. Should interactions not be found to be statistically significant, we will fit a main effects-only model and use it to formally evaluate confounding by applying a change-in-estimates approach, with a 10% change in estimates being an initial screening criterion. **Secondary outcomes:** Similar procedures will be undertaken to assess intervention effects for the other EHR derived outcomes (documented orders for resuscitation preferences, palliative care consults, hospice enrollment, and documented health care proxies).

For our primary analysis, we will consider our primary outcome (ACP documentation) and our secondary outcomes (resuscitation preferences, palliative care, hospice use, and health care proxies) only for the patient's index hospitalization. However, because we expect some patients to have multiple rehospitalizations during the same step and may also include intervention time (i.e., crossover design), we will perform secondary analyses on all of our primary and secondary outcomes for each patient reviewing all EHR records from the index hospitalization of the patient until their death (or through study period). We will also perform stratified sensitivity analyses of patients who contribute only to control period vs. patients who contribute only to intervention period vs. those that contribute to both control and intervention periods.

We will conduct the above analyses on all Aim 1 and Aim 2a patients for the study primary and secondary outcomes.

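### The one-year hospice hypothesis cannot be tested with the planned data: the main analysis stops at index discharge, and later follow-up relies on the two hospitals' own records

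*Combined protocol and SAP*

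**What the plan says.** - **Hypothesis.** Sections 4.1 and 12.1 both state that more intervention-phase patients will "enroll in hospice over the course of one year of follow-up". The Aim 1 hypothesis as repeated in section 12.3 gives no time window for hospice.
- **Main analysis.** Section 12.3 takes the primary outcome and all secondary outcomes, hospice included, "only for the patient's index hospitalization".
- **Secondary analysis.** The same section adds an analysis of every outcome for each patient, "reviewing all EHR records from the index hospitalization of the patient until their death (or through study period". Its stated reason is that some patients will be rehospitalized.
- **Data source.** Section 12.3: "All data regarding Aim 1 will come from the EHR". Section 11.2: "Source documents for this study will consist of electronic health record (EHR) data from each data collection site". Section 9, under NLP data collection, is narrower: "the inpatient EHR records (including those with ADRD/Delirium) will be analyzed".
- **Chart review.** The manual review in section 9 does collect discharge disposition, but only for Aim 2a patients whose caregiver was surveyed, and only for that stay.
- **Model.** Logistic regression for correlated binary data (GEE or random effects), with similar procedures for the secondary outcomes. No censoring rule is given.

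**The concern.** A patient can be discharged home, enrol with a community hospice and die there without contact with either study hospital. Nothing in the plan ensures that this enrolment, or the death that is meant to close the follow-up window, reaches the study data. A note search that finds nothing ordinarily returns no rather than missing, so the multiple imputation in section 12.3 would not address it.

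Whether a later event is seen depends on the patient's return to a study hospital. Hospice enrolment and a preference for less aggressive care could plausibly change how often patients return, so ascertainment may be linked to the effect being tested. Giving every patient the same follow-up window would not remove this. At stake is the interpretation of hypothesis 4: a weak or null follow-up result could not be told apart from under-ascertainment.

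**Working it through.** The plan gives no hospice rate, readmission rate or power statement for hospice, so there is no figure of its own to reproduce. The check sets the sections side by side and then illustrates the effect with assumed rates.

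**1. Which analysis addresses one year?** The main analysis ends at index discharge. Only the secondary analysis extends beyond it, so it alone can bear on hypothesis 4.

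**2. What can that analysis see?** At most, what is in the two sites' EHR. Section 9 speaks of inpatient records and section 12.3 of all EHR records. On the narrow reading, a later event is seen only around a readmission. On the broad reading, outpatient or telephone notes at the same sites also count. Neither reading systematically captures hospice arranged in the community. The documents do not say how deaths after discharge are found.

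**3. Incomplete capture.** Let p be the true proportion with post-discharge hospice and c the share visible at the sites. The recorded proportion is p × c. Assume p = 10% in control and 15% in intervention, a true difference of 5.0 points.

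| Capture, control / intervention | Recorded | Difference |
|---|---|---|
| 20% / 20% | 2.0% vs 3.0% | 1.0 point |
| 40% / 40% | 4.0% vs 6.0% | 2.0 points |
| 60% / 60% | 6.0% vs 9.0% | 3.0 points |
| 40% / 30% | 4.0% vs 4.5% | 0.5 points |
| 40% / 20% | 4.0% vs 3.0% | −1.0 point |
| 30% / 40% | 3.0% vs 6.0% | 3.0 points (ratio 2.0, true ratio 1.5) |

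Equal capture shrinks the difference and leaves the ratio at 1.5. Unequal capture can push the ratio either way. The recorded difference reaches zero when intervention capture is 10/15 = 67% of control capture.

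**4. A model on the narrow reading.** Assumed yearly hazards after index discharge: readmission r = 0.6, death d = 0.25, community hospice h = 0.08. Assumed chance of hospice at a readmission discharge: q = 0.06. Let λ = rq + h + d and A = (1 − e^−λ)/λ. One-year true enrolment is (rq + h)A. Enrolment seen at a readmission is rqA, ignoring the few community enrolments revealed by a later readmission.

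- Control: rq = 0.036, λ = 0.366, A = 0.837. True 0.116 × 0.837 = 9.7%; seen 0.036 × 0.837 = 3.0%.
- Intervention multiplies community hospice only by 1.5 (h = 0.12): λ = 0.406, A = 0.822. True 0.156 × 0.822 = 12.8%; seen 0.036 × 0.822 = 3.0%. True difference 3.1 points, seen about 0.
- Intervention multiplies both channels by 1.5 (h = 0.12, q = 0.09): rq = 0.054, λ = 0.424, A = 0.815. True 0.174 × 0.815 = 14.2%; seen 0.054 × 0.815 = 4.4%. True difference 4.5 points, seen 1.4.

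The model was also run by simulation over 16 combinations: r 0.6 or 1.2, h 0.03 or 0.08, q 6% or 10%, and readmission hazard after community enrolment multiplied by 0.2 or 1.0, with mean survival of 60 days after that enrolment. Control-phase capture was 32% to 83%. Recorded differences were:

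- community channel only: −0.1 to +0.4 points, against true gains of 1.1 to 3.2;
- both channels: +1.4 to +4.6 points;
- both channels with 15% fewer readmissions in the intervention phase: +0.7 to +2.6 points.

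**The case against.** The strongest reply is that the main analysis already confines hospice to the index stay, so only a supplementary analysis is affected. That is correct and limits the point. It does not rescue hypothesis 4, which is stated twice over one year and which the main analysis does not address.

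A reader might infer that later hospice is visible only on readmission. That rests on the word inpatient in section 9, which could simply mean records of patients admitted to hospital, while section 12.3 refers to all EHR records. The inpatient reading is likelier, because rehospitalization is the stated reason for the analysis, but it is not settled. Likewise, that every patient stays in the denominator and is scored no is a fair inference from uncensored yes/no models, not something the plan states.

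A reader might also infer that a real gain in hospice use would vanish or reverse. In the model this happens when the intervention raises community enrolment alone. This intervention is delivered in hospital, with hospice videos and prompts for palliative consults, so an effect on hospice at a later hospital discharge is just as plausible; the recorded difference then stays positive, though smaller. The model also starts at index discharge and omits index-stay hospice, which the planned analysis would see.

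Finally, ACP documentation, resuscitation orders and consults are defined by what is in the record. For these, absence is a true no, and the issue is unequal opportunity to record a yes, not missed events.

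**Conclusion.** The concern holds for post-index hospice use and for hypothesis 4 as worded. With no outside hospice or death source, one-year hospice enrolment is under-counted. The between-phase difference is likely attenuated, and may be biased in either direction if return to a study hospital differs by phase. The size cannot be given: every rate in the illustrations is an assumption, and the capture range is not a bound. The documents do not support a claim that the effect will disappear or change sign. The conclusion assumes that the named sources are complete and that an unseen enrolment is scored no. The primary endpoint and all index-stay analyses stand.

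**What to change.** 1. In sections 4.1 and 12.1, restate hypothesis 4 as hospice referral or enrolment by discharge from the index hospitalization, which matches the main analysis in section 12.3. Ascertain it from index-stay notes plus the structured discharge disposition, pulled for all Aim 1 patients rather than only for the Aim 2a chart-review group.
2. Reconcile section 9 (inpatient records) with section 12.3 (all EHR records), and state which note types are searched after the index stay.
3. In section 12.3, label post-index hospice as hospice documented at study sites, report it beside readmissions per patient by phase, and draw no conclusion from it about true one-year hospice use. Formal follow-up analysis of the other outcomes may stay.

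The cost is protocol wording, one extra structured EHR field in the existing extracts, and giving up the one-year hospice claim. No extra patients are needed.
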